## **8.2.1. CRESS**

The primary efficacy endpoint is the proportion of responders on  $\geq 3$  of 5 items at week 24 using CRESS. CRESS has been developed to assess treatment efficacy in participants with pSS. CRESS consists of the following items, with definitions of treatment response and lower disease activity:

- Systemic disease activity: as measured with clinESSDAI (Section 8.2.4)
  - Response is defined as a score of < 5 points.
- Patient-reported symptoms: as measured with ESSPRI (Section 8.2.6.1)
  - Response is defined as a decrease of  $\geq 1$  point or  $\geq 15\%$  from baseline.
- Tear gland function: as measured with Schirmer's test (Section 8.2.7.3) and OSS (Section 8.2.7.4)
  - If Schirmer's test is ≤ 5 mm at baseline (abnormal), a response is defined as an increase of at least 5 mm from baseline. OR
  - If OSS is ≥ 3 points at baseline (abnormal), a response is defined as a decrease of at least 2 points from baseline. OR
  - If both OSS and Schirmer's scores are normal at baseline, a response is defined as no change that results in an abnormal OSS or Schirmer's score.
- Salivary gland function: as measured with UWSF (Section 8.2.7.1) and SGUS
  - UWSF: at least 25% increase in score, or if score is 0 mL/min at baseline, any increase from baseline OR
  - SGUS: at least 25% decrease in total Hocevar score from baseline
- Serology: as measured with serum IgG and RF
  - RF: Decrease of at least 25% from baseline OR
  - IgG: Reduction of at least 10% from baseline

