## 9.3.2. Primary Endpoint Analysis

The primary endpoint is response on  $\geq 3$  of 5 items of CRESS at week 24. The 5 items are systemic disease activity (clinESSDAI), patient-reported symptoms (ESSPRI), tear gland function (Schirmer's test, OSS), salivary gland function (UWSF, SGUS), and serology (serum IgG and RF).

A 95% Wilson Score CI for the proportion of CRESS responders will be presented for both treatment groups. This will be provided for all full analysis set participants and by IgG stratum at screening (> 16.0 g/L or  $\leq 16 \text{ g/L}$ ) for the efgartigimod treatment group.

Additionally, the CRESS response will be analyzed between efgartigimed and placebo using the full analysis set by means of a Cochran-Mantel-Haenszel test, stratified by IgG value at screening (> 16.0 g/L or  $\leq 16 \text{ g/L}$ ). The common odds ratio will be provided, along with the 95% CI.

In the event of missing values for the primary endpoint, only those participants who have a week 24 value will be included in the primary analysis. A sensitivity analysis, treating those participants with missing week 24 data as nonresponders, will be included.

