## 9.3.3. Secondary Endpoint Analyses

The proportion of responders at week 24 in the clinESSDAI and ESSPRI components of the CRESS will be analyzed using the same approach as the overall CRESS response. The ESSDAI and STAR responder endpoints will be analyzed similarly.

Descriptive summaries by time point of the CRESS components, the ESSDAI and STAR scores, their changes, and percent changes from baseline will be provided, as appropriate. Estimates of the differences in response between treatment groups will be provided based on an analysis of covariance (ANCOVA), or suitable alternative, approach.

The histological parameters, relative counts of lymphocytic infiltrate (stained for CD45), and B/B+T cell ratio will be summarized descriptively as raw counts and their changes from baseline.

Full details of the secondary analyses will be included in the SAP.

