efgartigimod IV compared to placebo on clinical efficacy parameters	
 
improvement in EULAR Sjögren's syndrome disease activity index (ESSDAI): improvement of ≥ 3 points in ESSDAI score at week 24
 
Proportion of participants with low disease activity: ESSDAI score of < 5 at week 24
 
Proportion of participants with minimal clinically important improvement in clinESSDAI: improvement of ≥ 3 points in clinESSDAI score at week 24
 
Proportion of participants with low disease activity: clinESSDAI score of < 5 at week 24
 
Proportion of participants with minimal clinically important improvement in ESSPRI: decrease of 1 point or ≥ 15% at week 24
 
Change in ESSDAI score at week 24
 
Change in clinESSDAI score at week 24
 
Change in ESSPRI score at week 24
 
Change in ESSPRI score at week 24
 
			
To evaluate the effect of efgartigimod IV compared to placebo on STAR	
 
Proportion of participants with Sjögren's Tool for Assessing Response
 
(STAR) score of ≥ 5 at week 24
 
			
To evaluate the PK of efgartigimod IV	Efgartigimod serum concentration-time profile			
To evaluate the PD of efgartigimod IV	
 
Values, changes from baseline, and percent reduction from baseline in total IgG levels in serum
 
Values, changes from baseline, and percent reduction from baseline in
 
			

Document:

Author:

Version Number:

V2.0

Version Date: 31JAN2024

Template No.: CS\_TP\_BS016 Revision 7 Reference: CS\_WI\_BS005

Effective Date: 01Nov2021

Statistical Analysis Plan

Page 14 of 78

Objectives	Endpoints
	autoantibodies in serum:  - Anti-Ro/SS-A  - Anti-La/SS-B
To evaluate the immunogenicity of efgartigimod IV	Incidence and prevalence of antidrug antibody(ies) (ADA) against efgartigimod in serum
Exploratory	
s	•
	•

Template No.: CS\_TP\_BS016 Revision 7

Reference: CS\_WI\_BS005

Version Number:

Version Date:

V2.0

31JAN2024

Effective Date: 01Nov2021

Document: Author:

Statistical Analysis Plan

Page 15 of 78

Objectives	Endpoints
	•
	•

**Table B:** Estimands

Objectives		
	Main	Supplementary

Document:
Author: Version Number: V2.0

Version Date: 31JAN2024

Template No.: CS\_TP\_BS016 Revision 7 Reference: CS\_WI\_BS005

Effective Date: 01Nov2021

Statistical Analysis Plan

Page 16 of 78

	Treatment conditions	Treatment conditions

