#### 14.2. Secondary Efficacy

The secondary efficacy analyses will be performed for the EAS and will be analyzed on data observed.

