#### Statistical Analysis Plan

Page 49 of 78

Biological [1]	No=0	Absence of any of the following biological features
	Low=1	Clonal component and/or hypocomplementemia (low C4 or C3 or CH50) and/or hypergammaglobulinemia or high IgG level between 16 and 20 g/L
	Moderate=2	Presence of cryoglobulinemia and/or hypergammaglobulinemia or high IgG level > 20 g/L, and/or recent onset hypogammaglobulinemia or recent decrease of IgG level (< 5 g/L)

The proportion of efgartigimod and placebo participants with improvement of >= 3 points in score and the proportion of participants having ESSDAI score of <5 at week 24 will be provided, along with 95% Wilson Score CIs by each IgG stratum at screening (> 16.0 g/L or  $\leq$  16 g/L) for both treatment groups and for each of these two endpoints.

# 14.2.1.2 Proportion of Participants with Minimal Clinically Important Improvement in clinESSDAI: Improvement of ≥ 3 Points in clinESSDAI Score at Week 24 and Proportion of oParticipants with Low Disease Activity: clinESSDAI score of < 5 at Week 24

As explained in Section 14.1.1 of SAP, the ClinESSDAI includes all ESSDAI domains except the biological domain.

The proportion of efgartigimod and placebo participants with improvement of  $\geq$  3 points in clinESSDAI score and the proportion of participants having clinESSDAI score of  $\leq$  5 at week 24 will be provided, and along with 95% Wilson Score CIs by each IgG stratum at screening ( $\geq$  16.0 g/L or  $\leq$  16 g/L) for both treatment groups and for each of these two endpoints.

### 14.2.1.3 Proportion of Participants with Minimal Clinically Important Improvement in ESSPRI: Decrease of 1 Point or ≥ 15% at Week 24

The Information on the derivation of ESSPRI total score is provided in Section 14.1.1.

The proportion of participants with decrease of 1 point or  $\geq$  15% in ESSPRI total score at week 24 will be provided and along with 95% Wilson Score CIs by each IgG stratum at screening ( $\geq$  16.0 g/L or  $\leq$  16 g/L) for both treatment groups and for each of these two endpoints.

#### 14.2.1.4 Change in ESSDAI Score, clinESSDAI Score and ESSPRI Score at Week 24

These scores will be descriptively summarized for actual scores and changes from baseline scores for each visit and by treatment.

Document:

Author:

Version Number: V2.0

Version Date: 31JAN2024

Template No.: CS TP BS016 Revision 7 Reference: CS WI BS005

Effective Date: 01Nov2021

Statistical Analysis Plan

Author:

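### The SAP does not carry forward the protocol's comparison with placebo for four secondary responder endpoints, and neither document explicitly names one for clinESSDAI improvement of at least 3 points

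*SAP*

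**What the plan says.** SAP section 2, Table A, states the objective behind these endpoints as the effect of "efgartigimod IV compared to placebo on clinical efficacy parameters". SAP 14.2.1.1 (two ESSDAI endpoints), 14.2.1.2 (two clinESSDAI endpoints) and 14.2.1.3 (ESSPRI) each promise proportions "along with 95% Wilson Score CIs by each IgG stratum at screening", for both treatment groups. None mentions an odds ratio, a risk difference or a CMH analysis, and none refers to the primary endpoint for its method of analysis. SAP 14.2 adds: "The secondary efficacy analyses will be performed for the EAS and will be analyzed on data observed".

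The protocol asks for more. Section 9.3.3 says that week 24 response in the clinESSDAI and ESSPRI components of CRESS "will be analyzed using the same approach as the overall CRESS response", and then: "The ESSDAI and STAR responder endpoints will be analyzed similarly". Section 9.3.2 defines that approach. It has Wilson intervals for both groups ("This will be provided for all full analysis set participants and by IgG stratum at screening", the by-stratum part for efgartigimod only) and a between-arm analysis "by means of a Cochran-Mantel-Haenszel test, stratified by IgG value at screening", reported as a common odds ratio with 95% CI.

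Elsewhere the SAP does specify comparisons. STAR (14.2.1.6) and the stricter cut-offs in 14.4.1 to 14.4.3 are expressly tied to the primary endpoint's method. The continuous ESSDAI, clinESSDAI and ESSPRI scores have a mixed-model (MMRM) treatment difference with 95% CI in 14.2.1.4.

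**The concern.** Protocol 9.1 describes an estimation study meant to give first evidence of efficacy over several clinical endpoints, and protocol 4.2 says the totality of endpoints will be used to judge treatment response. An endpoint that is to be compared with placebo needs a named effect measure and interval. Separate per-arm intervals do not supply one: a reader cannot obtain a confidence interval for a treatment effect from whether two such intervals overlap.

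If the SAP is programmed as it reads, these responder tables will carry no treatment effect, and any measure added later will have been chosen after unblinding. The SAP is also uneven: the stricter cut-offs in 14.4, labelled sensitivity analyses, inherit the primary endpoint's comparison, while the secondary endpoints on the same scales do not.

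**Working it through.** **Which endpoints have a contrast, and where**

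| Endpoint | SAP 14.2.1.1 to 14.2.1.3 | Protocol 9.3.3 |
|---|---|---|
| ESSDAI improvement of at least 3 | none named | as CRESS (ESSDAI responders) |
| ESSDAI below 5 | none named | as CRESS (ESSDAI responders) |
| clinESSDAI below 5 | none named | as CRESS (CRESS component) |
| ESSPRI response | none named | as CRESS (CRESS component) |
| clinESSDAI improvement of at least 3 | none named | not named |

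The last row follows from protocol 8.2.1, where the clinESSDAI item of CRESS is a threshold: "Response is defined as a score of < 5 points". Improvement of at least 3 points is therefore not a CRESS component, and the sentence in 9.3.3 does not reach it.

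**The plan's own figure.** Protocol 9.5 gives a one-sided 95% Wilson lower bound of about 33% for 50% of 20. With p = 0.5, n = 20, z = 1.645:

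[p + z²/2n − z√(p(1−p)/n + z²/4n²)] / (1 + z²/n) = (0.5676 − 0.1960)/1.1353 = 0.327.

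The figure reproduces.

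**Precision by stratum and pooled.** Inputs: about 15 participants per IgG stratum and 2:1 allocation (protocol 9.5), hence about 10 efgartigimod and 5 placebo per stratum. The responder counts are assumed, because the documents give no rates for these five endpoints. Two-sided 95% Wilson intervals (z = 1.96):

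- one stratum: 5/10 gives 24% to 76%; 2/5 gives 12% to 77%; 1/5 gives 4% to 62%
- pooled: 10/20 gives 30% to 70%; 3/10 gives 11% to 60%

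**The estimate the protocol calls for.** The Mantel-Haenszel odds ratio is Σ(ad/N) / Σ(bc/N), where a, b are efgartigimod responders and non-responders, c, d are the same for placebo, and N = 15 per stratum. For 5/10 versus 1/5 and 5/10 versus 2/5:

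- numerator: (5×4)/15 + (5×3)/15 = 35/15
- denominator: (5×1)/15 + (5×2)/15 = 15/15
- odds ratio: 35/15 = 2.33
- Robins-Breslow-Greenland standard error of the log odds ratio: 0.82; 95% CI 0.46 to 11.7

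Keeping efgartigimod at 5/10 in both strata, placebo 1/5 in each gives 4.0 (0.67 to 23.7), and 2/5 in each gives 1.5 (0.32 to 7.0).

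**When the odds ratio fails.** If no placebo participant responds, c = 0 in both strata, the denominator is zero and there is no estimate. Borrowing the 24% to 32% placebo rates that protocol 9.5 cites for CRESS, the chance of this with 10 placebo participants is 0.76¹⁰ = 0.064 down to 0.68¹⁰ = 0.021. The true rates for these endpoints may differ.

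**The case against.** The strongest reply is that the two documents should be read together. The SAP is based on protocol version 2.0 and elaborates it, so the odds ratio in protocol 9.3.2 could be taken to apply still. This stands to a degree. A reader might infer from the SAP alone that no comparison exists anywhere for the five endpoints; that is too strong, because the protocol specifies one for four of them. It does not remove the gap: the SAP states its own analysis for each endpoint and stops short of the protocol's, although it links STAR and 14.4 to the primary method.

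Three further inferences are tempting and not supported.

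- **An undisclosed departure.** Protocol section 9 says method changes will be described in the SAP, and the readable part of SAP 3.4 does not list this one. But that list is incomplete in the public copy, so an entry cannot be ruled out.
- **Pooled intervals dropped.** Read literally, the text gives 5 × 2 × 2 = 20 per-arm, per-stratum intervals and nothing overall. But STAR uses almost the same by-stratum phrase and is declared identical to the primary analysis, so the phrase does not exclude pooled intervals. Copied wording is plausible: the ESSPRI paragraph refers to two endpoints where there is one.
- **CRESS itself left unstratified.** SAP section 2 calls the IgG-stratified CMH an additional sensitivity analysis, and 14.1.1 mentions an unadjusted odds ratio. But Table B names CMH under both estimands, 14.1.1 promises a common odds ratio, and the surrounding text and code are not visible. No conclusion should be drawn.

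It is also fair that the practical weight is limited. There is no formal hypothesis, p-values are supportive only, and all three scales have an MMRM treatment difference. That bears on the size of the point, not on whether it exists.

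**Conclusion.** The point holds as a mismatch between SAP and protocol that should be reconciled. The visible text of SAP 14.2.1.1 to 14.2.1.3 omits the between-arm analysis that protocol 9.3.3 sets for four responder endpoints, and no contrast is explicitly named in either document for the fifth. Whether pooled intervals are planned is unclear.

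The consequence is modest. No data are lost, since pooled and stratified results could be rebuilt from counts by arm and stratum. No error rate is at stake in a study without a formal hypothesis. The missing estimate would be wide (for example 2.33, 0.46 to 11.7), but it would show what the data can and cannot exclude. Those figures assume an even split across strata, no missing data and illustrative counts. Confidence is medium, because parts of SAP 3.4 and of sections 14.1.1 and 14.2 are not visible.

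**What to change.** In SAP 14.2.1.1 to 14.2.1.3, state for each of the five endpoints:

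1. Wilson 95% intervals per arm, overall and by screening IgG stratum.
2. The CMH common odds ratio for efgartigimod versus placebo, stratified by screening IgG (above 16.0 versus at most 16 g/L), with 95% CI.
3. That both are calculated on the observed-data basis already set in SAP 14.2. A bare cross-reference to the primary endpoint would leave this open, because the primary analysis counts participants with intercurrent events as non-responders.
4. What is reported if the odds ratio cannot be estimated because no placebo participant responds. A risk difference is one option: 10/20 versus 3/10 gives 20 points, Newcombe 95% CI −16 to 48.

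If omitting the comparison is intended, list it in SAP 3.4 as a change from protocol 9.3.3. The cost is a few lines of SAP wording and reuse of the CRESS and STAR table shells. No new data are needed.

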#### 14.3. Exploratory Efficacy

The exploratory efficacy analyses will be performed for the EAS.

In each Section 14.3.x that relates to continuous parameters, the actual and change from baseline to week 24 analysis; for each visit will be descriptively summarized only.

[figure not shown]

Effective Date: 01Nov2021

Statistical Analysis Plan

Page 53 of 78

[figure not shown]

Effective Date: 01Nov2021

Statistical Analysis Plan

Page 54 of 78

Effective Date: 01Nov2021

Effective Date: 01Nov2021

ArgenX PROTOCOL ARGX-113-2106

Statistical Analysis Plan Page 55 of 78 14.3.7. 14.3.8. 14.3.9. Document: Author: Version Number: V2.0 31JAN2024 Version Date: Template No.: CS\_TP\_BS016 Revision 7 Reference: CS\_WI\_BS005

Statistical Analysis Plan

ArgenX PROTOCOL ARGX-113-2106

Page 56 of 78

14.3.10. 14.3.11. 14.4. **Additional Efficacy Analysis** The below mentioned endpoints will be performed as sensitivity analysis:

Document:

Author:

Version Number:

V2.0

Version Date:

31JAN2024

Template No.: CS\_TP\_BS016 Revision 7 Reference: CS\_WI\_BS005

Effective Date: 01Nov2021

Statistical Analysis Plan

Page 57 of 78

### 14.4.1. Proportion of participants with MCII in clinESSDAI defined as improvement of ≥ 4 points in clinESSDAI at week 24

As explained in Section 14.1.1 of SAP, the ClinESSDAI includes all ESSDAI domains except the biological domain.

The proportion of efgartigimod and placebo participants with MCII in clinESSDAI of >= 4 points in clinESSDAI score at week 24 will be provided, along with 95% Wilson score CIs and by each IgG stratum at screening (> 16.0 g/L or  $\leq$  16 g/L) for both treatment groups, in an identical manner to the primary endpoint.

### 14.4.2. Proportion of participants with MCII in ESSDAI defined as improvement of ≥ 4 points in ESSDAI at week 24

As explained in Section 14.1.1 , the ESSDAI (Seror [a], et al., 2015)10 consists of 12 domains, 11 related to organ involvement (cutaneous, pulmonary, renal, articular, muscular, peripheral nervous system, central nervous system, hematological, glandular, constitutional, and lymphadenopathic) and 1 biological domain reflecting B-cell activity.

The proportion of efgartigimod and placebo participants with MCII in ESSDAI of >= 4 points in at week 24 will be provided, along with 95% Wilson score CIs and by each IgG stratum at screening (> 16.0 g/L or  $\le 16$  g/L) for both treatment groups, in an identical manner to the primary endpoint.

### 14.4.3. Proportion of participants with MCII in ESSPRI defined as decrease of ≥ 1.5 points

The Information on the derivation of ESSPRI total score is provided in Section 14.1.1.

The proportion of participants with decrease of  $\geq$  1.5 points in ESSPRI total score at week 24 will be provided and along with 95% Wilson score CIs and by each IgG stratum at screening ( $\geq$  16.0 g/L or  $\leq$  16 g/L) for both treatment groups, in an identical manner to the primary endpoint.

#### 15. PHARMACODYNAMIC ANALYSIS

PD analyses will be performed in the SAF. PD endpoints include IgG autoantibodies. PD endpointswill be summarized using descriptive statistics at each analysis visit. Actual values, changes from baseline, and percent

Document:

Author:

Version Number:

V2.0

Version Date:

31JAN2024

Template No.: CS TP BS016 Revision 7 Reference: CS WI BS005

Effective Date: 01Nov2021

Statistical Analysis Plan

Page 58 of 78

change from baseline will be presented. In addition to the planned time points, the following time points will also be shown:

- Maximum drop from baseline
- Minimum postbaseline value

Additionally, a line chart showing percent change in Total IgG, over time will be prepared. If appropriate, the graphic presentation of percent change over time may be presented for all PD endpoints combined. All PD data will be listed.

#### 16. IMMUNOGENICITY ANALYSIS

Incidence and prevalence of ADAs against efgartigimod will be assessed in the SAF. ADAs to efgartigimod is measured at the time points specified in the schedule of activities of protocol, primarily at baseline, week 2, 4, 8, 12, 16, 24, EDV and SFV.

Immunogenicity samples are analyzed in a 3-tiered approach:

- All samples are evaluated in the ADA screening assay and are scored ADA screening positive (tier 1) or negative.
- If a sample is scored positive in the ADA screening assay, it is further evaluated in the confirmatory assay (tier
   2) and is scored confirmed positive (positive immuno-depletion) or confirmed negative (negative immuno-depletion).
- If a sample is scored as confirmed positive, the samples are further characterized in the ADA titration assay (to determine titer).

If available, a titer result will be reported for the ADA confirmed positive samples. However, a titer result is not always available:

- If the ADA confirmed positive sample could not be run in the titration assay (e.g., due to insufficient sample volume/quality to perform the titer analysis), the result will be described as "positive immuno-depletion", and the sample should be considered ADA positive.
- If a sample is negative in the titration assay, it will be reported as "negative titer", but it should be considered ADA positive because it was confirmed positive in the second tier.
- If a sample could not be analyzed or reported as "positive screen", the ADA sample status is ADA unevaluable An overview of this 3-tiered approach and all possible ADA sample results that will be reported by the laboratory is

Document:

Author:

Version Number:

V2.0

Version Date:

31JAN2024

Template No.: CS TP BS016 Revision 7 Reference: CS WI BS005

Effective Date: 01Nov2021

[figure not shown]

Statistical Analysis Plan

Page 59 of 78

given below. From these reported ADA sample results, a final ADA sample status must be derived during the statistical analysis, as presented in the final column ("Final ADA Outcome"):

Figure 2: ADA Sample Status

<sup>a "Positive titer" is reported if it was not possible to retrieve a numerical value.

#### Participant Classification for ADA Against Efgartigimod

TableH below gives an overview of how the ADA participant classification will be derived, starting from the participant baseline ADA sample status.

Document:
Author:

Version Number: V2.0
Version Date: 31JAN2024

Template No.: CS\_TP\_BS016 Revision 7 Reference: CS\_WI\_BS005

Effective Date: 01Nov2021

Statistical Analysis Plan

Page 60 of 78

Table H: Participant Classification for ADA Against Efgartigimod

		Highest a postbaseline sample status				
Participant ADA classification	ADA negative	ADA positive (missing titer b )	ADA positive (negative titer c or numerical titer value)	ADA unevaluable		
Baseline ADA sample status						
ADA negative	ADA negative	Treatment- induced ADA	Treatment-induced ADA	ADA unevaluable		
ADA positive (missing titer b )	Treatment- unaffected ADA	ADA unevaluable	ADA unevaluable	ADA unevaluable		
ADA positive (negative titer c or numerical titer value)	Treatment- unaffected ADA	ADA unevaluable	Titer <4x	ADA unevaluable		
ADA unevaluable	ADA unevaluable	ADA unevaluable	ADA unevaluable	ADA unevaluable		

a Highest sample status, with order (from low to high): ADA unevaluable, ADA negative, ADA positive ("positive immuno-depletion" or "positive titer"), ADA positive with titer <1 ("negative titer"), ADA positive with titer ≥1 (numerical value selecting the sample with highest titer).

The following definitions will be used in the summary tables:

- ADA evaluable participant = participant classified in any of following categories: ADA negative, treatment-unaffected ADA, treatment-induced ADA, or treatment-boosted ADA. The first 2 categories are classified as "ADA negative", and the latter 2 are classified as "ADA positive".
- ADA incidence = percentage of participants with treatment-induced or treatment-boosted ADA (denominator: number of evaluable participants).
- ADA prevalence = percentage of participants with treatment-unaffected ADA, treatment-induced ADA, or treatment-boosted ADA (denominator: number of evaluable participants).
- ADA unevaluable participant = participant classified as ADA unevaluable or with missing baseline ADA sample or without postbaseline ADA samples (in case no ADA data are available at all, the participant cannot

Document:
Author:

Version Number:
V2.0
Version Date: 31JAN2024

Template No.: CS\_TP\_BS016 Revision 7 Reference: CS\_WI\_BS005

Effective Date: 01Nov2021

<sup>b Samples with missing titer will have a reported ADA result of "positive immuno-depletion" or "positive titer".

c Results reported as "negative titer", i.e. titer value <1 will be set to a value of 1.

Statistical Analysis Plan

Page 61 of 78

be classified)

Note: A 4-fold difference in titer values is considered significant if a 2-fold serial dilution is applied (= 2 times the dilution factor).

**Frequency tabulations** (number and percentages) will be provided with ADA negative/positive/unevaluable samples per visit.

Frequency tabulations (number and percentages) will be provided in 1 table for:

- ADA unevaluable Participants
- ADA baseline positive/negative/unevaluable samples
- Participants per ADA participant classification
- Prevalence and incidence of ADA

**Correlation tables** by ADA against efgartigimod participant classification will be provided for the following parameters:

- Mean drug concentration over time
- Mean percent change from baseline in [total IgG]
- ClinESSDAI score at over time
- TEAEs by MedDRA SOC and PT
- Serious TEAEs by MedDRA SOC and PT
- Injection/infusion-related reactions

ADA against efgartigimod titer values will be summarized using descriptive statistics by ADA participant classification at each analysis visit.

All available data for ADA against efgartigimod will be listed, while also showing the ADA sample status and participant classification.

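### ADA prevalence (SAP section 16, Table H): participants confirmed positive both before and after dosing are dropped when a titer is missing, which lowers the estimate

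*SAP*

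**What the plan says.** Incidence and prevalence of ADA are a secondary endpoint (Protocol section 3, Table 1; SAP section 2, Table A).

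- **Sample level (SAP section 16).** If a confirmed-positive sample cannot be run in the titration assay, the result is reported without a titer, "and the sample should be considered ADA positive".
- **Participant level (SAP Table H).** Baseline status is crossed with the highest postbaseline status. For a participant who is positive at baseline without a titer, the row reads, for postbaseline negative, positive without titer, positive with titer, and unevaluable: "Treatment- unaffected ADA ADA unevaluable ADA unevaluable ADA unevaluable".
- **Who is evaluable.** "ADA evaluable participant = participant classified in any of following categories: ADA negative, treatment-unaffected ADA, treatment-induced ADA, or treatment-boosted ADA". The unevaluable group is defined as "participant classified as ADA unevaluable or with missing baseline ADA sample or without postbaseline ADA samples".
- **Prevalence.** "ADA prevalence = percentage of participants with treatment-unaffected ADA, treatment-induced ADA, or treatment-boosted ADA (denominator: number of evaluable participants"). Incidence uses the same denominator but counts only induced and boosted ADA.

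Section 16 also plans per-visit sample status, baseline status, the number of unevaluable participants, every participant class, and a full listing.

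**The concern.** A titer is needed to decide whether a baseline-positive participant was boosted by treatment or unaffected. That distinction matters for incidence. It does not matter for prevalence, which adds the two classes together. A single unevaluable class nevertheless serves both measures, so a missing titer removes people whose ADA status is already known to be positive.

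The rule is also inconsistent. A participant who is positive at baseline without a titer and negative afterwards is treatment-unaffected, and so counts as prevalent. A participant with the same baseline result who is positive afterwards is dropped. More evidence of ADA takes the participant out of the count.

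At stake is the headline value of a stated secondary endpoint in an arm of about 20, where one person is visible in the percentage.

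**Working it through.** The plan states no ADA rate, so there is no figure to reproduce. The check is a cell count followed by arithmetic on assumed counts.

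**Step 1: Table H as a map.** In the supplied text the titered/titered cell shows only its under-4-fold branch. I take it to split into unaffected and boosted at a 4-fold change, in line with the note on titer differences, and do not treat it as an error.

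| Baseline | Post negative | Post positive, no titer | Post positive, titer | Post unevaluable |
|---|---|---|---|---|
| Negative | negative | induced | induced | unevaluable |
| Positive, no titer | unaffected | **unevaluable** | **unevaluable** | unevaluable |
| Positive, titer | unaffected | **unevaluable** | unaffected or boosted | unevaluable |
| Unevaluable | unevaluable | unevaluable | unevaluable | unevaluable |

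Ten of 16 cells are unevaluable:

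- 3 (bold) hold two confirmed positives and lack only a titer.
- 4 hold one positive and one unevaluable status.
- 2 hold one negative and one unevaluable status.
- 1 holds nothing evaluable.

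3 + 4 + 2 + 1 = 10.

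**Step 2: direction in the three bold cells.** Let P be the ever-positive participants among N, and k those in the bold cells. The SAP value is (P − k)/(N − k), and

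P/N − (P − k)/(N − k) = k(N − P) / [N(N − k)],

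which is positive whenever P < N. The error is downward with certainty.

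**Step 3: size.** N = 20 is the efgartigimod number in the sample-size section. P and k are assumptions.

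| P | Full value | k = 1 | Fall | k = 2 | Fall |
|---|---|---|---|---|---|
| 3 | 3/20 = 15.0% | 2/19 = 10.5% | 4.5 points | 1/18 = 5.6% | 9.4 points |
| 5 | 5/20 = 25.0% | 4/19 = 21.1% | 3.9 points | 3/18 = 16.7% | 8.3 points |
| 8 | 8/20 = 40.0% | 7/19 = 36.8% | 3.2 points | 6/18 = 33.3% | 6.7 points |

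**Step 4: expected size in large samples.** Assume 10% are positive at baseline, 20% of the rest become positive, and 80% of baseline positives stay positive. True prevalence is 0.10 + 0.90 × 0.20 = 28.0%.

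- Titer missing for 10% at baseline and for 5% postbaseline (no titered positive): lost share = 0.10 × 0.80 × (1 − 0.90 × 0.95) = 0.0116. SAP value = (0.28 − 0.0116)/(1 − 0.0116) = 27.2%.
- Missing for 30% and 10%: lost share = 0.08 × (1 − 0.70 × 0.90) = 0.0296. SAP value = 0.2504/0.9704 = 25.8%.

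**Step 5: missing or unevaluable pair.** Here positives and negatives can both be lost. With 5 positives of 20 (25.0%):

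- losing 1 positive gives 4/19 = 21.1%;
- losing 1 negative gives 5/19 = 26.3%;
- losing 1 positive and 3 negatives gives 4/16 = 25.0%.

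From a true 28.0%, losing 20% of positives and 5% of negatives gives 0.224/(0.224 + 0.684) = 24.7%. The reverse gives 0.266/(0.266 + 0.576) = 31.6%. If loss is unrelated to status, the value stays at 28.0%.

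**The case against.** **A reader might infer that Table H always biases prevalence downward**, since 7 of the 10 unevaluable cells contain a confirmed positive. The documents do not support this. Four of those seven arise from an unevaluable pair, and on that route Table H also drops participants whose only evaluable status is negative. The definition of unevaluable likewise removes anyone lacking a baseline or any postbaseline sample, whatever the other sample shows. Direction there depends on who has missing data. The seven-cell count is also a count of table cells, not of participants.

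**A reader might also infer that any missing titer removes a participant.** It does not. A baseline-negative participant who is positive afterwards without a titer is counted as induced, and a baseline-positive participant without a titer who is negative afterwards is counted as unaffected.

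**The effect may be small.** Postbaseline status is the highest over repeated visits, with unevaluable ranked lowest and untitered positives ranked below titered ones, so one titered positive rescues the postbaseline side. Immunogenicity is descriptive (Protocol section 9.3.6), the study has no formal hypothesis (section 9.1), and precision is low anyway: a 95% Wilson interval for 4/20 runs from about 8% to 42%. The planned tables and listing let a reader find the excluded positives.

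All of this limits the size of the problem, and the first two points limit its scope. None of it repairs a missing baseline titer: Protocol section 8.9 assigns screening immunogenicity samples to method validation or future research, so no backup is planned. The displays expose the dropped positives but leave the reported prevalence uncorrected.

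**Conclusion.** The rule is wrong as written for three cells of Table H. Participants confirmed positive at both baseline and postbaseline are certain contributors to prevalence, and excluding them for want of a titer lowers the estimate. This follows from the SAP's own definitions and needs no outside source.

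The size rests on assumptions, because the documents give neither ADA nor missing-titer rates. With 20 efgartigimod participants and 3 to 8 ever-positive, one affected participant lowers prevalence by about 3 to 5 points. If no baseline-positive participant lacks a needed titer, the effect is nil. No direction of bias is claimed for missing or unevaluable pairs. Incidence is not in question: without the titer, boosted cannot be told from unaffected. The consequence is modest, but the endpoint is a stated one and the correction is simple.

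**What to change.** 1. **Prevalence only:** count every participant with confirmed-positive samples at both baseline and postbaseline in numerator and denominator, whether or not a titer is available. Keep these participants unevaluable for incidence. In the example above, 4/19 = 21.1% returns to 5/20 = 25.0%.
2. **Sensitivity prevalence:** participants with any confirmed-positive sample, divided by all participants with at least one evaluable ADA sample. It treats someone with a single negative sample as negative, so it belongs beside the main figure and does not replace it.

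The main prevalence should not be widened to readmit positives with an unevaluable pair while negatives in the same position stay out. With 5 positives among 20 and 20% of each group lacking a pair (1 positive, 3 negatives), the current rule gives 4/16 = 25.0%, the true value. The one-sided rule would give 5/17 = 29.4%.

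**Cost:** one changed definition, one derivation and one added sensitivity line, with no new data. Incidence and prevalence would have slightly different denominators, which needs a footnote, and reported prevalence may be slightly higher.
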